With more than seven million HIV-infected people,¹ South Africa is home to more people living with HIV than any other country in the world,² and their national ART program is the world's largest.² South Africa adopted a "treat all" policy to provide ART to all HIV-positive people, regardless of CD4+ cell count, in September 2016.³ Expanded ART availability has dramatically altered the health and quality of life of people living with HIV/AIDS, with an estimated life expectancy gain of 11.3 years between 2003 and 2011 due to ART⁴ and a 77% decrease in HIV transmission in stable serodiscordant couples.⁵ However, the rapid scale-up of the national ART program has put tremendous pressure on the limited resources of a public health sector that is hurrying to meet this immense need, and despite widespread availability of ART, over 135,000 people died of AIDS-related causes in 2016 in South Africa.¹ HIV and tuberculosis (usually exacerbated by HIV) are the top two causes of death among women ages 15-44 in South Africa.⁶ The potential for improved health through expanded ART availability will only be realized if individuals sustain engagement in HIV care.

Black African women of reproductive age (ages 20-34) are the population most heavily affected by the South African HIV epidemic, with 31.6% prevalence.⁷ Access to ART for all HIV-positive pregnant women through Option B+ has helped to reduce mother-to-child transmission of HIV to the point where near-elimination is now thought possible.⁸ Despite this astounding achievement, there is mounting evidence that women who initiate ART during pregnancy may be at very high risk of loss to follow-up (LTFU),⁹⁻¹² with re-engagement in routine HIV care after delivery a particular concern.^{13,14} The problem of patient LTFU within the public sector in South Africa has been well documented.^{15,16} Our earlier research conducted in South Africa found that 25.2% of women pregnant at ART initiation were LTFU after one year, compared to 15.8% of men and 11.1% of non-pregnant women.¹⁰ Our work also has helped to pinpoint the timing of LTFU to after delivery: among women diagnosed with HIV during antenatal care in Johannesburg, 47.9% were lost within six months of delivery;¹³ in Cape Town, disengagement was over twice as frequent in the postpartum period as during antenatal care.¹⁷

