	Q1	Q2	Q3	Q4	Q1	Q2	Q3	Q4	Q1	Q2	Q3	Q4
Study preparation												
IRB approval and renewal												
ClinicalTrials.gov registration												
Develop study instruments and REDCap database												
Adapt CareConekta smartphone app												
Confirm eligibility, recruit and consent participants												
Enrollment questionnaire												
Participant follow-up												
Follow-up questionnaire												
File review												
Data analysis												
Manuscript preparation												
R01 submission and revision												

STUDY DESIGN

Sample Size

We will enroll 200 participants.

For this pilot trial formal sample size estimation was not conducted. The sample size was reached based on the feasible enrolment from the study site within the study timeline. Approximately 4,000 women seek antenatal care at the MOU annually; ~30% of these are HIV-positive, about 1 200 per year, or 100 per month. Our formative work (HREC REF 792/2016 and 227/2017) showed that over half of these women own smartphones. If we conservatively estimate that 30% of all pregnant, HIV-positive women seeking antenatal care each month will be eligible and interested which equals 30 participants enrolled per month. We anticipate that it will take approximately seven months to reach our enrolment target of 200 participants (see Timeline above).

Based on our earlier work in South Africa and at the study site, we estimate that 25% of the participants will engage in long-distance travel during the study period. A sample size of 200 allows us to characterize the mobility experiences of 50 women who travel and explore differences with those who do not. While we do not anticipate having sufficient power to detect statistically significant differences between groups in Aims 2b, the information gained through this pilot study will inform sample sizes for larger future studies should this pilot show promise.

Study arms

- **Control arm (n=100):** Participants will receive standard CareConekta, which will track their mobility and allow the participant to look up new ART facilities upon request.
- **Intervention arm (n=100):** Participants will receive standard CareConekta with the following additions:
 - text notifications of nearby ART facilities when they have traveled >50 km from the study site for >7 days

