The selection of participants will be equitable in relation to the research purpose and setting because any interested woman attending antenatal services at the study clinic who meets the eligibility criteria will be invited to enroll. Pregnant women will be limited by gestational age to the third trimester to allow for a nine-month total follow-up time within the time constraints of this three-year grant. In South Africa, most women present for their first antenatal visit around 20 weeks gestation or later,^{13,44,45} and attendance for antenatal visits is generally high,^{13,17} so we do not believe there will be substantial bias introduced by enrolling women later in pregnancy. isiXhosa is the predominant language in the region of the study site, and English also is widely spoken, so we do not anticipate excluding potential participants due to language. Basic smartphone-level literacy will be required of participants in order to assess the impact of messages. However, we anticipate that most women who own a smartphone already have a basic smartphone-level literacy ability. We acknowledge that women who own a smartphone may be different than those who do not, in terms of employment, education, or other factors. Besides the additional financial resources needed to provide phones, we want to be able to assess CareConekta in existing phones for maximal impact. If women already have a smartphone (over half of the population), providing a second phone for study purposes is redundant and burdensome. For women who do not already own a smartphone, we are concerned with ethical implications of providing such a highly-desired item as a smartphone in terms of possible coercion for study participation, the impact it may have on relationships between participants and partners and/or friends, and the potential for disclosure for participating in an HIV-related study.

In order to assess differences between our cohort of smartphone users and the general population assessed for eligibility, we will collect four demographic indicators at the time of recruitment: age, education, employment and nationality. These will be collected anonymously prior to study enrollment or the collection of any identifying data.

Informed consent

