To assess engagement in HIV care, we will report retention in care, which will be assessed at the six-month postpartum point and defined as no documented HIV-specific contact with any healthcare facility (including medication pick-ups) for >3 months. We also will report viral suppression six months after delivery, using thresholds of ≤ 50 and ≤ 1000 copies/ml. Additionally, we will report vertical HIV transmission and completion of the routine 10-week infant PCR test.

We will fit a series of models of mobility metrics on outcomes. For one, we will use a dichotomous exposure of mobility (any travel >50 km: yes/no), we will use Cox proportional hazard regression models to estimate the association of mobility on these outcomes, and will produce adjusted hazard ratios and 95% confidence intervals for retention in care and achieving viral suppression. We also will identify other predictors of engagement in HIV care. We will produce crude Kaplan-Meier curves to time to loss to follow-up and time to viral suppression by mobility group. Additionally, we will perform sensitivity analyses to explore how the estimated effect size changes when using varying cut-off points to define mobility.

Aim 2a. To assess the acceptability and feasibility of the standard and enhanced app, with a focus on identifying user preference and implementation outcomes.

Outcome: Acceptability and feasibility of CareConekta

Acceptability and feasibility data will be collected among all 200 participants. Those in the intervention arm will receive additional questions related to the enhanced app features. The outcomes selected for analysis in Aim 3a correspond with the Technology Acceptance Model for Resource-Limited Settings (TAM-RLS) framework, which was designed to draw attention to end-user acceptability as a predictor of mHealth technology adoption in low-resource settings.⁴⁶ We will report proportions and 95% confidence intervals for categorical variables and medians and interquartile ranges for continuous variables. For open-ended questions, we will create a list of categorical themes that emerge over multiple readings and calculate the proportions for the response categories. We will select key illustrative quotes for each theme.

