Aim 2b. To evaluate the initial efficacy of the enhanced CareConekta intervention, using notifications and staff contact to improve engagement in HIV care, by assessing the association between study arm and engagement in HIV care at six-months postpartum.

Outcome: Efficacy of the intervention

The overall efficacy analysis will include participants in both arms (n=200). To assess overall cohort engagement in HIV care, we will report retention in care, which will be assessed at the six-month postpartum point and defined as no documented HIV-specific contact with any healthcare facility (including medication pick-ups) for >3 months. We also will report viral suppression six months after delivery based on the viral load test closest to the six-month period, using thresholds of ≤50 and ≤1000 copies/ml. Additionally, we will report vertical HIV transmission and completion of the routine 10-week infant PCR test.

Study arm assignment is the primary exposure of interest. We will use Cox proportional hazard regression models to estimate the association of study arm assignment on these outcomes, and will produce adjusted hazard ratios and 95% confidence intervals for retention in care and achieving viral suppression by study arm. We also will identify other predictors of engagement in HIV care. We will produce crude Kaplan-Meier curves to time to loss to follow-up and time to viral suppression by study arm. In a secondary analysis, we will perform an as-treated analysis using self-reported data regarding actually reading the notifications and/or WhatsApp messages or staff phone calls to analyze the effect of receiving the intervention.

HUMAN SUBJECTS' PROTECTION

Ethical review process

The research protocol will be reviewed by the Institutional Review Boards at Vanderbilt University; the University of California, San Francisco; and the University of Cape Town in South Africa. All research activities will occur in South Africa. All procedures will conform to U.S. and South African ethical standards for human subjects' research.

Informed consent

Informed consent will be obtained for all participants as described in the "Informed Consent" section above.

Privacy and confidentiality

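### Aims 1b and 2b define retention in care by the criterion for non-retention, so the outcome as written runs opposite to its label

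*Combined protocol and SAP*

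**What the plan says.** Under Analysis Plan and Study Outcomes, Aim 1b (control arm only) and Aim 2b (both arms) use the same sentence. Each will report "retention in care, which will be assessed at the six-month postpartum point and defined as no documented HIV-specific contact with any healthcare facility". The sentence goes on to include medication pick-ups among the contacts and to set the gap at more than three months.

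Both sections then plan Cox models. In Aim 2b these yield adjusted "hazard ratios and 95% confidence intervals for retention in care and achieving viral suppression by study arm"; Aim 1b has the matching plan by mobility. The accompanying curves are named differently. Aim 2b says "We will produce crude Kaplan-Meier curves to time to loss to follow-up and time to viral suppression by study arm", and Aim 1b says "We will produce crude Kaplan-Meier curves to time to loss to follow-up and time to viral suppression by mobility group".

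Elsewhere retention is a good outcome: the Study Aims list it with viral suppression as a form of engagement in HIV care. Loss to follow-up appears in the Introduction as background, without a gap length, start date or event date. File review activities mentions participants lost from the study, but that is study attrition.

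**The concern.** The criterion attached to *retention* is the absence of contact, which identifies women who are not retained. The document contains no other definition that would override it.

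The error reaches the analysis through the labels. For viral suppression, a hazard ratio above 1 is favourable. A reader will take the retention hazard ratio, promised in the same sentence, the same way. If the event modelled is the written gap, a helpful intervention gives a ratio below 1, which under that label looks like harm.

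Initial efficacy is part of the primary objective in the Abstract, and Sample Size says that "the information gained through this pilot study will inform sample sizes for larger future studies should this pilot show promise". The retention figure and its definition are therefore what later planners would carry forward.

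**Working it through.** The plan states no figure that depends on this definition, and Sample Size says that no formal calculation was made. The check is therefore textual, with an illustration of size.

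**1. The texts side by side (Aims 1b and 2b)**

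| Element | What is written | Direction |
|---|---|---|
| Study Aims | retention is a form of engagement | favourable |
| Outcome rule | no contact for more than 3 months | unfavourable |
| Cox label | hazard ratio for retention | favourable |
| Kaplan-Meier event | time to loss to follow-up | unfavourable |

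The rule agrees with the Kaplan-Meier event and contradicts its own label.

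**2. Effect on the reported proportion.** Let L be the true proportion lost and R = 1 − L the true proportion retained. Literal coding prints L as retention, so the error is R − L. The Introduction gives two loss rates, both from other cohorts: "25.2% of women pregnant at ART initiation were LTFU after one year" and, for women diagnosed during antenatal care in Johannesburg, "47.9% were lost within six months of delivery".

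- L = 0.252: R = 1 − 0.252 = 0.748. Printed 25.2%, true 74.8%. Error 0.748 − 0.252 = 0.496, or 49.6 points; about 25 instead of 75 women in an arm of 100.
- L = 0.479: R = 1 − 0.479 = 0.521. Printed 47.9%, true 52.1%. Error 0.521 − 0.479 = 0.042, or 4.2 points; about 48 instead of 52 women in an arm of 100.

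**3. Effect on a comparison.** With true retention r1 and r0 in the two groups, literal coding reports (1 − r1) − (1 − r0) = −(r1 − r0). The size is kept and the sign is reversed, whatever the values.

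To put numbers on this, assume a hazard ratio for loss of 0.7 (not in the documents) and take loss under intervention as 1 − (1 − L)^0.7:

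- L = 0.252: 1 − 0.748^0.7 = 0.184. True effect on retention +6.8 points; as written −6.8.
- L = 0.479: 1 − 0.521^0.7 = 0.366. True effect on retention +11.3 points; as written −11.3.

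**4. Effect on power.** The variance of a proportion, p(1 − p), is unchanged when p is replaced by 1 − p. With 100 per arm and an assumed two-sided 0.05, a two-proportion test has power 0.213 and 0.363 in these two cases under either coding.

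**5. What relabelling leaves open.** Moved to loss to follow-up, the sentence supplies the gap length and the qualifying contacts. It does not supply a time origin, an event date or a censoring rule. Selection of study participants sets the gestational-age limit "to allow for a nine-month total follow-up time within the time constraints of this three-year grant", so a gap can open and close before the six-month point. Take a woman last seen at month 1 postpartum who returns at month 5. She has contact in the last three months, so she is retained at month 6. Under a first-gap rule she also has a loss event, dated month 1 if the last contact is used or month 4 if the day the gap reaches three months is used. If only a gap still open at month 6 counts, she has none.

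**The case against.** The strongest reply is that the meaning is obvious. Retention is grouped with engagement throughout, the curves are named for loss, and the more-than-three-months sentence is most naturally the loss definition under the wrong label. An analyst who codes women without contact as retained is possible but unlikely, and at a loss rate near 25% the printed figure would look wrong and be caught. Only near 50% would the number hide the reversal. The illustration is simply one minus background rates from other cohorts, one of them measured at one year. Sample Size already disclaims adequate power for Aim 2b.

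Most of this stands, and it limits the harm. It does not remove the error: the rule is written backwards twice and corrected nowhere. Inferring the direction also does not say which event the Cox model uses or when it occurs.

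A reader might infer more than the documents support:

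- *That loss to follow-up is a second, wholly undefined outcome.* Relabelling recovers its gap and contacts; what remains is under-specification.
- *That the look-back for the six-month status is open.* A gap assessed at that point most naturally means one current then. The ambiguity belongs to the time-to-event analysis.
- *That the delivery date is in conflict.* File review activities uses estimated delivery only to set the earliest review for women who do not return. The follow-up phone call collects the infant's date of birth, and Aim 1a names sources for the delivery date, though for timing travel.
- *That the study-triggered viral load inflates retention.* It could do so only if laboratory tests count as contact and the draw falls in the look-back. Neither is stated, and the size is unknown.

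**Conclusion.** The definition is wrong as written in both aims and should be corrected before analysis. Followed literally, it reports the complement of retention, reverses the sign of any arm or mobility difference, and makes a beneficial hazard ratio read as harm. The complement and the sign change are exact. The 49.6-point and 4.2-point errors only illustrate size and assume the cited background loss rates; the 6.8-point and 11.3-point effects also assume a hazard ratio of 0.7.

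The documents do not show that anyone intends to code the outcome backwards, and no stated figure, sample size or power depends on it. This is a correctable error in an outcome definition, with some missing time-to-event detail. It is not a design failure.

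**What to change.** In both Aim 1b and Aim 2b, replace the sentence with: *Retained at six months postpartum: at least one documented HIV-specific contact (including medication pick-ups) in the 3 months ending at the six-month postpartum point. Not retained: no such contact in that window.*

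Attach the more-than-three-months gap to loss to follow-up. Use that one event in both the Cox model and the Kaplan-Meier curves, and label the hazard ratio as being for loss to follow-up. In Aim 2b a ratio below 1 then favours the intervention; in Aim 1b a ratio above 1 means mobility goes with loss.

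In the same edit, state:

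- the time origin for each aim (randomization for Aim 2b), and whether antenatal or enrolment visits count as contact, so that no event is dated before the origin;
- the event date, and censoring at the six-month point;
- how deaths are handled, since File review activities captures facility-recorded deaths;
- whether laboratory tests count as contact. Visit and dispensing data cover only the Western Cape while laboratory records are national, so this could decide the status of women who leave the province.

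Whether a later return undoes a loss event is the sponsor's choice of estimand; a first-gap rule is one option. If it is chosen, the report should explain that some women will be retained at six months and still have a loss event. A note on whether study-triggered viral loads count as contact is optional.

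The cost is a few sentences in two sections. Enrolment, visits and sample size do not change.

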Mobility data will be collected throughout the follow-up period. Geospatial coordinates will be recorded with a timestamp. Upon bulk extraction of these data, we will import location information as decimal degree coordinates into ArcMap spatial analysis software. Data charges related to the app are reverse-billed through our app development consultants to ensure timely transmission of data with no cost to participants.

Weekly raffle incentive

To encourage participants to keep the CareConekta app installed on their phone and the GPS function enabled throughout the entire study period, we will offer an incentive: a weekly raffle of one 200MB data bundle (worth approximately \$4). Participants will be eligible to enter the raffle if their phone sent GPS coordinates at least once per day for the prior week. Winners will be randomly selected among all eligible participants using a randomization code automated in STATA. The weekly raffle incentive will only apply to participants enrolled from October 2020 onwards and who have signed version 5.0 or later of the Informed Consent document. There is no limit to the number of times a participant may win the raffle.

Six-month postpartum follow-up visit procedures

Recontacting participant

All participants will be recontacted six months postpartum to return to the study site for a one-time visit. A minimum of three contact attempts by phone and/or home visit will be made for each participant. All contact attempts (successful or not) will be recorded on a contact log.

Follow-up questionnaire

Study staff will complete a face-to-face questionnaire with each participant. This follow-up questionnaire will include reasons for overall acceptability of CareConekta (standard or enhanced), reasons for travel and clinic switching, and barriers and facilitators to care since the start of the study. Response options primarily will be categorical, with open-ended questions to allow for deeper elaboration. Additional questions will be asked of participants in the intervention arm regarding acceptability and feasibility of the intervention. Responses will be recorded directly into a REDCap database by an interviewer using a tablet computer or laptop. This questionnaire may be conducted telephonically.

Viral load testing and potential blood draw

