In routine care in this setting, viral load tests are to be repeated every three months in pregnancy and every six months during breastfeeding, so we expect that most women will have a routine viral load completed before six months postpartum. To avoid additional blood draws for the participant, at the follow-up visit, the study staff will check NHLS to determine the most recent viral load test. If the participant has had no viral load test within 3 months prior to the six-month study follow-up visit, a blood draw for viral load will be conducted by the clinical staff at the Gugulethu CHC. A clinic nurse will collect 5 ml of venous blood, which will be transported daily to the National Health Laboratory Services (NHLs) for HIV viral load testing (Abbott Molecular RealTime HIV-1 assay (Abbott Molecular, Illinois, USA). We will not recontact participants about viral load results unless participants are on ART and the viral load result indicates lack of viral suppression. In that case, results will be made available to participants over the phone (or in person, at participant's wish) with appropriate referrals. For all participants, viral load results will be captured using the participants provincial folder number into the NHLs database, as is standard practice for routine laboratory results in South Africa.

Uninstall app

During the follow-up visit, the CareConekta app will be uninstalled from each participant's phone.

Reimbursement

After all the above steps are complete, the enrollment visit will conclude with providing the participant R150 reimbursement for transport and missed opportunity costs. Payment will be made in cash and/or grocery vouchers and will be recorded in a reimbursement log.

File review activities

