Electronic and paper files will be reviewed after the participant's final visit to assess engagement in HIV care. If the participant fails to return for a final visit, files will be reviewed a minimum of seven months after estimated delivery. Electronic data on health facility visits and pharmacy dispensing, including facility recorded deaths, will be requested the Provincial Health Data Centre of the Western Cape Department of Health by providing a list of folder numbers of women who have consented and enrolled in the study. These data include all public health facilities in the Western Cape Province, which is the location of the study site. Laboratory records, including viral loads, from any South African facility will be abstracted from the NHLS database. Participants in both arms who are lost from the study at the time of study close will be traced through staff outreach and electronic/paper medical records. Informed consent will include permission to link with electronic medical records.

Table of schedule of measures

Item for completion	Enrolment	Early postpartum phone call	6 months postpartum
Eligibility Checklist	x		
Informed Consent	x		
Linkage form	x	x child details	
Randomisation log	x		
Demographics and medical history	x		x
Maternal mobility (past and planned)	x		x
Maternal clinic switching	x		x
Perceived barriers and facilitators of engagement in care	x		x
Depression (PHQ-4)	x		x
Alcohol and drug use (AUDIT-C and DUDIT Q1)	x		x
Patient provider relationship scale	x		x
ART adherence	x		x
WHO VAW (intimate partner violence)	x		
Social impact scale (stigma)	x		
Availability of social support	x		
Life events (trauma)			x
Infant health			x
Child mobility			x
Acceptability of CareConekta			x
Impact of COVID-19 & lockdown of HIV care and mobility			x
Laboratory tests			
HIV viral load*			x
Record review			
Antenatal and obstetric information	x	x	x
ART pharmacy records	x	x	x
Maternal laboratory results	x	x	x
Child HIV testing		x	x

* If no routine viral load result found in the three months before the study visit

DATA COLLECTION AND STORAGE

Data collection methods

Data will be collected in three ways:

- Face-to-face enrollment and follow-up questionnaires

- Medical record review (electronic and paper file records) to determine participant engagement in HIV care
- Electronic app usage and mobility data

Questionnaire data

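### Aim 2b takes the viral load closest to six months with no window, so a woman with no postpartum test would be scored on an antenatal result

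*Combined protocol and SAP*

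**What the plan says.** - **Aim 2b, efficacy outcome.** Suppression is "viral suppression six months after delivery based on the viral load test closest to the six-month period", "using thresholds of ≤50 and ≤1000 copies/ml". The analysis set is all 200 women. No earliest date, latest date or postpartum-only condition is given, and nothing is said about a woman with no test near six months.
- **Aim 1b.** The wording is only: "We also will report viral suppression six months after delivery, using thresholds of ≤ 50 and ≤ 1000 copies/ml". There is no rule for choosing among several tests.
- **Viral load testing and potential blood draw.** In routine care, "viral load tests are to be repeated every three months in pregnancy and every six months during breastfeeding". The study draw has this trigger: "If the participant has had no viral load test within 3 months prior to the six-month study follow-up visit". Clinical staff at the Gugulethu health centre carry it out.
- **Follow-up questionnaire.** "This questionnaire may be conducted telephonically". No blood draw is described for a phone contact.
- **File review activities.** A woman who does not come back has her files reviewed no earlier than seven months past the estimated delivery date. "Laboratory records, including viral loads, from any South African facility will be abstracted from the NHLS database", with no date limit stated.

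**The concern.** The only time limit in the plan, the 3-month look-back, decides who is bled at the follow-up visit. It does not decide which results count as the six-month outcome. The reported proportion can therefore mix two quantities: postpartum suppression in women who attend or remain in care somewhere, and antenatal suppression in women with no later test.

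The second group is likely to include women who left care after delivery, which is the event the intervention is meant to prevent. A woman who was suppressed in pregnancy and then stopped attending could be counted as suppressed at six months. The protocol says the pilot will inform the sample size of later trials, so a distorted proportion could carry forward.

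**Working it through.** The documents state no expected suppression rate, missed-visit rate or power for this outcome, so there is no figure of the plan's own to reproduce. Two checks are possible.

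**1. How old can the selected test be?** Inputs: enrolment from 28 weeks of gestation (inclusion criteria), three-monthly routine tests in pregnancy, and assessment at six months postpartum, taken as 26 weeks. Delivery at 40 weeks is assumed.

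Gap in weeks = (40 − gestational age at test) + 26; months = weeks / 4.345.

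- Test at 28 weeks: 12 + 26 = 38 weeks, or 8.7 months.
- Test at 32 weeks: 8 + 26 = 34 weeks, or 7.8 months.
- Test at 36 weeks: 4 + 26 = 30 weeks, or 6.9 months.
- Latest possible antenatal test, at 40 weeks: 0 + 26 = 26 weeks, or 6.0 months.

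Antenatal results should be on file, since the schedule of measures has maternal laboratory results reviewed from enrolment. If a woman has no postpartum test, one of these is her closest test.

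**2. What could that do to the proportion?** Let f be the share of a group whose closest test is antenatal, a the share of those women suppressed at that test, and t the share of them truly suppressed at six months. Then:

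overstatement = f × (a − t)

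None of these inputs is in the documents. Assume a from 0.7 to 0.9 and t from 0.3 to 0.7. The difference a − t then runs from 0.7 − 0.7 = 0 to 0.9 − 0.3 = 0.6.

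- f = 10%: 0 to 0.10 × 0.6, or 0 to 6 points.
- f = 20%: 0 to 0.20 × 0.6, or 0 to 12 points.
- f = 30%: 0 to 0.30 × 0.6, or 0 to 18 points.

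**Between arms.** If f, a and t are the same in both arms, the overstatement cancels in the difference. For an unequal case, assume f = 25% in control and 15% in intervention, a = 0.8, t = 0.4, and 0.85 suppressed among all other women.

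- True status: intervention 0.85 × 0.85 + 0.15 × 0.4 = 0.7825; control 0.75 × 0.85 + 0.25 × 0.4 = 0.7375; difference 4.5 points.
- Closest test: intervention 0.7225 + 0.15 × 0.8 = 0.8425; control 0.6375 + 0.25 × 0.8 = 0.8375; difference 0.5 points.
- No in-window test counted as not suppressed: 0.7225 − 0.6375 = 8.5 points.
- No in-window test excluded: 0.85 − 0.85 = 0 points.

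In this example the true difference lies between the last two figures, which is why both should be shown.

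**The case against.** Several points on the other side are sound and limit what can be claimed.

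- **Missing the visit is not enough.** A reader might infer that every woman who misses it is scored on a pregnancy result and counted as suppressed. Two further conditions are needed: no viral load nearer to six months, and an antenatal result at or below the threshold. NHLS covers any South African facility, so a woman in care elsewhere in the country may have a usable postpartum result. The plan expects most women to have a routine test before six months postpartum, makes at least three contact attempts (home visits are an option), and traces women lost at study close. These steps shrink the affected group. They do not remove it, because no blood draw is described outside the visit.
- **Aim 1b does not contain the rule.** A reader might infer that the mobility comparison is biased by it. The closest-test wording stands only in Aim 2b. In Aim 1b the fault is that no rule is stated; distortion would follow only if the same unlimited rule were used there and the share affected differed by mobility.
- **The Cox and Kaplan-Meier analyses.** A reader might infer that the hazard ratios are biased too. Both aims analyse time to suppression, and the plan does not say how a single closest test enters those models. The effect is shown only for the reported proportion.
- **Leaving care is not invisible.** Retention is a separate outcome based on documented facility contact, so disengagement can be seen there whatever viral load is selected.
- **The postpartum label.** Describing the outcome as six months after delivery signals the intent, but excludes no earlier test.
- **It is a pilot.** No formal sample size was set, adequate power for Aim 2b is not expected, and dated results can still be obtained from NHLS. This argues against treating the matter as critical, not against settling the rule before analysis.

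**Conclusion.** The point holds as a should-fix. Followed as written, the Aim 2b rule gives a wrong six-month classification basis for any woman with no postpartum viral load, using a result about 6 to 9 months too early (assuming term delivery and an on-schedule third-trimester test). That can overstate the reported suppression proportion among women who left care. It can also distort a comparison by arm, or by mobility if Aim 1b adopts the same rule, when the affected share differs between groups.

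The size cannot be derived from the documents. The illustrative 0 to 6 points at 10% affected and 0 to 18 points at 30% rest wholly on assumed suppression rates, and zero is within the range. The 47.9% loss after delivery quoted in the Introduction comes from an earlier Johannesburg study and is not this trial's share without a postpartum test, so it should not be used to fix the figure.

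**What to change.** In Aim 2b, and as the stated rule in Aim 1b:

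- Use the test closest to six months among postpartum tests in a stated window. One workable lower limit is 3 months after delivery, which matches the existing look-back for the study draw. Set the upper limit at a date that the file review or NHLS extraction actually covers for every woman.
- State that a test taken before or at delivery is never used.
- Report the number of women without an in-window test by arm and by mobility group.
- Show the suppression proportion with these women counted as not suppressed and with them excluded.
- State how the rule relates to the time-to-suppression analyses.

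The cost is mainly wording and one extra tabulation; no new study procedure is needed. Fewer women will have an evaluable result, and the suppression proportion may be lower. Because the plan allows non-attenders' files to be reviewed from seven months past the estimated delivery date, an upper limit beyond seven months may require a later NHLS extraction.
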